1.1 Aim

- Compare EMA outcome between the two arms across all responses to the 4 standard scenarios, looking at the time periods from baseline to 3 months and 3 months to 6 months.

2 Study Population

2.1 Inclusion Criteria

- 50+ years of age
- Mild to moderate, symmetrical SNHL (symmetrical: < 20 dB between ears on average from 500-4000 Hz)
- Open-mindedness to unilateral or bilateral amplification
- No prior hearing aid experience
- Adequate literacy to complete questionnaires
- Willing to purchase study-specific hearing aid(s)

2.2 Exclusion Criteria

- Concerns for middle ear pathology
- Concerns for retrocochlear pathology
- Severe tinnitus as the reason for seeking amplification
- Co-morbid condition that would interfere with study (e.g., dementia, blindness, neurologic pathology)
- History of fluctuating hearing loss

2.3 Data Acquisition

Fill in all relevant information:

Study design	Randomized controlled trial with 2 arms (bilateral hearing aid, unilateral hearing aid) Note: Randomization was stratified by clinical site.
Data source/how the data were collected	Screening information pulled from EHR data Baseline surveys captured via in-person interview and recorded in REDCap
Contact information for team member responsible for data collection/acquisition	All data access is through [REDACTED] [REDACTED]. Questions on data validity will go to PI: [name] ([contact])
Date or version (if downloaded, provide date)	10.17.2024
Data transfer method and date	Direct data extraction from REDCap
Where dataset is stored	REDCap Extracted data and analytic datasets are stored on a secure drive in the CRU folder: \\duhs-vclin-

3 Outcomes, Exposures, and Additional Variables of Interest

3.1 Outcome(s)

Outcome	Description	Variables and Source	Specifications
GHABP Unaided	GHABP is measured at baseline (unaided)	
GHABP unaided: ghabun1a – ghabun6c
 
3 total questions for each of 6 scenarios (4 standard, 2 user-nominated)
 
First question just asks if this scenario has happened – ONLY include those who say yes to this
	
For questions 2 and 3 (IF they answer yes to question 1), doing this separately by question:
 
 1. Subtract 1, multiply by 25, average answer to question across 4 standard scenarios 2. Subtract 1, multiply by 25, average answer to question across 2 user-nominated scenarios 3. Subtract 1, multiply by 25, average answer to question across all 6 scenarios. 
For self-nominated goals, people may write in “NA”, “N/A”, “Na”, “None”, “Not applicable” – these should be ignored (set to missing)

GHABP Aided	GHABP is measured at 3 months (aided)	
GHABP aided: ghaha1a_v1 – ghaha6f_v1
 
6 total questions for each of 6 scenarios (4 standard, 2 user-nominated)
 
First question just asks if this scenario has happened – ONLY include those who say yes to this
	
For questions 3-6 (IF they answer yes to question 1), doing this separately by question:
 
 1. Subtract 1, multiply by 25, average answer to question across 4 standard scenarios 2. Subtract 1, multiply by 25, average answer to question across 2 user-nominated scenarios 3. Subtract 1, multiply by 25, average answer to question across all 6 scenarios. 
Note: ignore current question 2 as it is non-standard

			
For self-nominated goals, people may write in “NA”, “N/A”, “Na”, “None”, “Not applicable” – these should be ignored (set to missing). Note: we will need to keep track of these baseline goals in case people answer “yes” at the later timepoints.

EMA	
EMA are surveys (same questions as GHABP) sent 5 times a day for a week. Have these in two time periods: before 3 months and after 3 months. These time periods will be kept separate.
	
EMA variables: for Duke, these are ghaba1a – ghaba6f. For Vanderbilt, these are ghaba1a_v2 – ghaba6f_v2. Have EMA “events” EMA 1a – EMA 7e for survey before 3 months. Have EMA “events” EMA 8a – EMA 14e for surveys after 3 months (before 6 months)
 
6 total questions for each of 6 scenarios (4 standard, 2 user-nominated)
 
First question just asks if this scenario has happened – ONLY include those who say yes to this
	
Several pieces here. First, for questions 3-6 (IF they answer yes to question 1), subtract 1 and multiply by 25.
 
Then interested in 2 cases:
 
 1. Look at answer to all question X's over ALL scenarios for blocks of scenarios below 2. For question X, look at answer to all question X's within a given scenario for the 4 standard scenarios 
Blocks of scenarios:
 
 1. 4 standard scenarios 2. 2 user-nominated scenarios 3. All 6 scenarios. 
Note: ignore current question 2 as it is non-standard
 
For self-nominated goals, people may write in “NA”, “N/A”, “Na”, “None”, “Not applicable” – these should be ignored (set to missing). Note: we will need to keep track of these baseline goals in case people answer “yes” at the later timepoints.

Notes: 6 total scenarios, 4 standard, 2 user-nominated. Standard scenarios:

1. LISTENING TO THE TELEVISION WITH OTHER FAMILY OR FRIENDS WHEN THE VOLUME IS ADJUSTED TO SUIT OTHER PEOPLE
2. HAVING A CONVERSATION WITH ONE OTHER PERSON WHEN THERE IS NO BACKGROUND NOISE

3. CARRYING ON A CONVERSATION IN A BUSY STREET OR SHOP
4. HAVING A CONVERSATION WITH SEVERAL PEOPLE IN A GROUP

Unaided questions:

1. Does this situation happen in your life?
2. How much difficulty do you have in this situation?
3. How much does any difficulty in this situation worry, annoy or upset you?

Aided/EMA questions:

1. Did this situation happen in the past few weeks? (GHABP aided) OR Did this situation happen in the last three hours? (EMA)
2. In this situation, with your hearing aid, how much does any difficulty in this situation worry, annoy or upset you? (NOTE: ignore this question as it is non-standard)
3. In this situation, what proportion of the time do you wear your hearing aid?
4. In this situation, how much does your hearing aid help you?
5. In this situation, with your hearing aid, how much difficulty do you now have?
6. For this situation, how satisfied are you with your hearing aid?

3.2 Additional Variables of Interest

Variable	Description	Variables and Source	Specifications
Randomization assignment	hearing aid assignment	Baseline visit: assign	Binary 1: unilateral 2: bilateral
Clinical site	Which site - Duke or Vanderbilt?	Baseline visit: which_site	Binary 1: Vanderbilt 2: Duke

4 Statistical Analysis Plan

Analysis: To be completed by December 31, 2024

4.1 Descriptive Characteristics for EMA Surveys

Analysis: We will present the mean with standard deviation (SD), median with interquartile range (IQR), and ranges (min and max) for number of EMA surveys completed. The 0-3-month period and 3-6-month period will be done separately, stratified by baseline assignment and 3M choice, respectively.

Table 1: EMA Summaries

Number of EMA Surveys Completed Before 3 Months	Assigned Unilateral (N=XXX)	Assigned Bilateral (N=XXX)
N	XXX	XXX
Mean (SD)	XXX (XXX)	XXX (XXX)
Median	XXX	XXX
Q1, Q3	XXX, XXX	XXX, XXX
Range	XXX - XXX	XXX - XXX
Number of EMA Surveys Completed After 3 Months	3M Choice – Unilateral (N=XXX)	3M Choice – Bilateral (N=XXX)
N	XXX	XXX

Mean (SD)	XXX (XXX)	XXX (XXX)
Median	XXX	XXX
Q1, Q3	XXX, XXX	XXX, XXX
Range	XXX - XXX	XXX - XXX

4.2 Aim: compare EMA surveys between the two arms in the period between baseline and 3 months, and between 3M choice groups between 3 months and 6 months

For question X, we want to look at the answers to all question X's over the 4 standard scenarios.

Analysis: This will be done using intent-to-treat for patients who have EMA surveys and answer "yes" to the first question (if the scenario happens). The primary analysis will be performed by linear mixed effects models with covariates clinical site and assigned treatment/3M choice, with a separate model for each question. The overall average of within-person means will be reported by treatment arm/3M choice, as well as T-test p-values from the fitted models for the treatment arm/3M choice covariate, where a p-value < 0.05 would indicate a difference in average response between treatment arms/3M choices.

Table 4: Repeated Measures ANOVA Comparing EMA Surveys Across Scenarios in Unilateral and Bilateral Groups

Question & Scenarios	Assigned Unilateral	Assigned Bilateral	P-Value*
	(Overall Mean)	(Overall Mean)	
0-3 Months			
1. In this situation, what proportion of the time do you wear your hearing aid?	XXX	XXX	XXX
2. In this situation, how much does your hearing aid help you?	XXX	XXX	XXX
3. In this situation, with your hearing aid, how much difficulty do you now have?	XXX	XXX	XXX
4. For this situation, how satisfied are you with your hearing aid?	XXX	XXX	XXX
3-6 Months			
1. In this situation, what proportion of the time do you wear your hearing aid?	XXX	XXX	XXX
2. In this situation, how much does your hearing aid help you?	XXX	XXX	XXX
3. In this situation, with your hearing aid, how much difficulty do you now have?	XXX	XXX	XXX
4. For this situation, how satisfied are you with your hearing aid?	XXX	XXX	XXX

[figure not shown]
[figure not shown]
*Using T-test statistic

4.3 Aim: compare EMA surveys between the two arms in the period between baseline and 3 months, and between 3M choice groups between 3 months and 6 months

For question X, we want to look at the answers to all question X's within a given scenario for the 4 standard scenarios.

Analysis: This will be descriptive. We will use boxplots, violin plots, or another type of plot to describe these scenarios. For each of the 4 standard scenarios, we will display the distributions of the answers to each of the 4 questions for both unilateral and bilateral hearing aid groups (i.e., 1 plot per question with two boxes per scenario for each of the 4 scenario/treatment combos).

Examples of what boxplots and violin plots look like (violin plots can be more informative about the distribution of data because they show the density as well):

5 Future Plans

There are additional items we may wish to explore in the future, at which point a new SAP will be developed. In particular, we may explore EMA responses for the 2 user-nominated scenarios or all 6 scenarios.

Statistical Analysis Plan (SAP) – Hearing Aid Choice and Switching

Project: Evaluation of Unilateral vs Bilateral Hearing Aids for the Treatment of Age-related Hearing Loss

IRB Number: Pro00106077

Investigator(s): [name], AuD, PhD

Biostatisticians: [REDACTED]

Original Creation Date: 11.16.2023

Version Date: 11.26.2024

Investigator Agreement

- All statistical analyses included in an abstract or manuscript should reflect the work of the biostatistician(s) listed on this SAP. No changes or additional analyses should be made to the results or findings without discussing with the project biostatistician(s).
- All biostatisticians on this SAP should be given sufficient time to review the full presentation, abstract, manuscript, or grant and be included as co-authors on any abstract or manuscript resulting from the analyses.
- If substantial additional analysis is necessary or the aims of the project change, a new SAP will need to be developed.
- Publications resulting from this SAP are supported in part by the Duke CTSA and must cite grant number UL1TR002553 and be submitted to PubMed Central.
- I have reviewed the SAP and understand that any changes must be documented.

Acknowledged by: Click or tap here to enter text.

Date: Click or tap to enter a date.

Activity Log

11.16.2023 Created SAP for outcomes related to hearing aid choice and switching
06.03.2024 Added additional variables, moved questions related to data collected after 3 months to the Future Plans section
07.11.2024 Resolved some comments, added details about potential covariates
07.25.2024 Moved 6-month APHAB into this SAP
10.02.2024 Resolved some comments after discussion (see previous SAP for more details), updated variable names/descriptions
11.26.2024 Resolved some comments after discussion, revised model for identifying associations between baseline covariates and 3M switching or 6M final choice

Acronyms

APHAB	Abbreviated Profile of Hearing Aid Benefit
EMA	Ecological Momentary Assessment
GHABP	Glasgow Hearing Aid Benefit Profile
IOI-HA	International Outcomes Inventory for Hearing Aids

SADL	Satisfaction with Amplification in Daily Life
SSQ	Speech Spatial Qualities
HHIE	Hearing Handicap Inventory for Elderly

1 Study Overview

Background/Introduction: The overall goal of the project is to determine the benefit of unilateral or bilateral hearing aid fittings in adults with mild-to-moderate age-related hearing loss. This will address the lack of high-quality evidence supporting bilateral hearing aids over unilateral hearing aids. This project will use a randomized controlled trial with two treatment arms: a bilateral hearing aid fitting group and a unilateral hearing aid fitting group.

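### The EMA SAP's aim promises a comparison by randomised arm in both periods, but the 3-6 month models group patients only by their own month-3 choice, under an unqualified intent-to-treat label

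*SAP*

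**What the plan says.** The EMA SAP has a single aim (section 1.1): "Compare EMA outcome between the two arms across all responses to the 4 standard scenarios". The same sentence applies this to two periods, one ending at month 3 and the other running from there to month 6. Read plainly, that is a comparison by randomised arm in each of two periods.

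Section 4.1 then sets a different grouping for each period. The EMA summaries are to be "stratified by baseline assignment and 3M choice, respectively", and the second block of Table 1 is headed accordingly ("3M Choice – Unilateral" and its bilateral counterpart). The heading of section 4.2 keeps the arm comparison for baseline to month 3 and makes the later comparison "between 3M choice groups between 3 months and 6 months". The method is "linear mixed effects models with covariates clinical site and assigned treatment/3M choice", with one model per question and a 0.05 threshold for either grouping.

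The population sentence in 4.2 starts "This will be done using intent-to-treat for patients who have EMA surveys and answer" and continues with the condition that the scenario occurred. It does not say which period it applies to. The results go into Table 4, titled "Repeated Measures ANOVA Comparing EMA Surveys Across Scenarios in Unilateral and Bilateral Groups". In the extracted text this table has one header row, by assignment, above both the 0-3 month and the 3-6 month rows.

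**The concern.** Month-3 choice is not a randomised grouping. Under the protocol's Month 3 Visit, patients may keep, change or return their aids after three months with the assigned configuration. A difference between choice groups therefore mixes any effect of one versus two aids with whatever led patients to choose. Intent-to-treat cannot describe such a contrast.

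Followed as written, the plan could report four p-values from a self-selected comparison as intent-to-treat, and possibly under randomised-arm column heads. The stated aim would meanwhile have no result for 3-6 months. The protocol counts ecological hearing aid outcomes among its primary objectives, so readers are likely to give these results weight.

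**Working it through.** The documents state no sample size, power or error rate for the EMA analysis, so there is no figure to reproduce. The check compares the texts and counts the planned models.

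**Step 1. Grouping by period**

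| Place in EMA SAP | 0-3 months | 3-6 months |
|---|---|---|
| 1.1 Aim | arms | arms |
| 4.1 text and Table 1 | assignment | month-3 choice |
| 4.2 heading | arms | month-3 choice |
| 4.2 population sentence | intent-to-treat | intent-to-treat (no period named) |
| Table 4 header, as extracted | assignment | assignment |

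Taken alone, the slash between assigned treatment and choice in the model statement could mean that both covariates enter every model. The 4.2 heading, together with the period-by-period mapping in 4.1, shows that one grouping is meant per period.

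**Step 2. Does another section or SAP supply the 3-6 month comparison by arm?**

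- EMA SAP 4.3 is descriptive and carries the same heading as 4.2.
- EMA SAP 5 (Future Plans) names only the user-nominated scenarios or all six scenarios.
- The 3-month SAP lists EMA surveys only as a possible future analysis.
- The 6-month SAP's outcome list (3.1) contains no EMA measure.

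None of them does.

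**Step 3. Count of models and p-values**

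- Table 4: 4 questions x 2 periods = 8 p-values.
- By assignment: 4 (0-3 months) + 0 (3-6 months) = 4.
- By month-3 choice: 0 + 4 = 4.
- 3-6 month models that answer aim 1.1: 0 of 4.
- p-values under a header that does not match their grouping, if Table 4 really has one header: 4 / 8 = 50%.

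**Step 4. Could choice and assignment coincide closely enough not to matter?** Section 4.4 of the 6-month SAP dropped its repeated-measures models partly because participants tended to switch configuration at month 3. The two groupings will therefore differ. No rate is given, so the extent is unknown.

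**Step 5. Who contributes 3-6 month data?** Under Phase 2 of the protocol, only patients who kept one or two aids are asked to repeat the EMA. Even a model by assigned arm would therefore not include everyone randomised.

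**Step 6. Are the inputs for an arm model available?** Assignment and site are listed in EMA SAP 3.2. The later EMA events run from 8a to 14e, which is 7 days x 5 surveys = 35 scheduled surveys per patient surveyed. No new collection is needed. Section 3.2 does not list a month-3 choice variable. It is defined in the choice and switching SAP (3.2) with five levels, including none and missing, and the EMA SAP does not say how these become two groups.

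**The case against.** The strongest reply is that the choice grouping is not hidden. It appears in 4.1, in Table 1, in the 4.2 heading and analysis paragraph, and in the 4.3 heading, so an analyst would know what was being fitted. It also follows the protocol, where secondary objective 2 and the Phase 2 description are about outcomes under the patient's final choice. On that view aim 1.1 is the outlier, and the matter is one sentence not updated and one loose label. An added arm model would not be intent-to-treat either, because only patients who kept an aid are surveyed. The 6-month SAP already compares APHAB, SADL, HHIE, IOI-HA and SSQ by arm. Finally, Table 4 is a blank shell read from a PDF, and a second header row may have been lost.

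Much of this stands. Grouping by choice is legitimate and openly stated, and it is not the fault here. Amending aim 1.1 would be enough to reconcile aim and analysis, and the added model has to be described with care. The table point should be checked against the PDF. It has some weight, because Table 1's second header came through extraction, but the finding does not depend on it.

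The reply does not remove two things: an aim with no matching analysis for 3-6 months, and an intent-to-treat label on a contrast to which it cannot apply. The 6-month SAP shows how to keep the two apart, by arm in its section 4.1 and by choice in its section 4.2.

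**Conclusion.** The concern holds. The aim, the analysis label and, as extracted, the Table 4 header do not match the 3-6 month analysis actually planned. Four of the eight EMA p-values come from a non-randomised contrast covered by an intent-to-treat statement, and none of the four 3-6 month models addresses aim 1.1. That second count needs no assumption about Table 4. The statement that half the p-values sit under the wrong header assumes that the PDF has a single header row.

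No bias or error rate can be attached, because switching and return rates are not given. The reach is the 3-6 month EMA analysis only. This should be corrected, since it decides what those p-values may be said to show, but it does not touch the primary result.

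**What to change.** 1. In EMA SAP 4.2, limit the intent-to-treat statement to the 0-3 month comparison by assignment.
2. Head the 3-6 month block of Table 4 by month-3 choice, as Table 1 already does, and describe that contrast as exploratory and non-randomised.
3. Add the same mixed model by assigned arm for 3-6 months. Call it a comparison by assignment among patients who kept an aid, not intent-to-treat. Report for each arm how many were not surveyed and how many did not respond. If this model is not wanted, amend aim 1.1 to say that 3-6 months is compared by choice only.
4. Optionally, cross-reference the month-3 choice variable from the choice and switching SAP and state how its none and missing levels are handled.

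The minimum cost is one qualifier, one table header and one sentence in the aim. Adding the arm comparison means four more models on data already in the collection plan, using an assignment variable that the EMA SAP already lists.

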1.1 Hearing Aid Switching Aims

- Explore if treatment assignment influences switching configuration at 3 months
- Explore what predicts switching at 3 months
- Describe patient characteristics for switchers vs. non-switchers
- Describe APHAB data (subscale and global score) over time within subgroups of individuals

2 Study Population

2.1 Inclusion Criteria

- 50+ years of age
- Mild to moderate, symmetrical SNHL (symmetrical: < 20 dB between ears on average from 500-4000 Hz)
- Open-mindedness to unilateral or bilateral amplification
- No prior hearing aid experience
- Adequate literacy to complete questionnaires
- Willing to purchase study-specific hearing aid(s)

2.2 Exclusion Criteria

- Concerns for middle ear pathology
- Concerns for retrocochlear pathology
- Severe tinnitus as the reason for seeking amplification
- Co-morbid condition that would interfere with study (e.g., dementia, blindness, neurologic pathology)
- History of fluctuating hearing loss

2.3 Data Acquisition

Fill in all relevant information:

Study design	Randomized controlled trial with 2 arms (bilateral hearing aid, unilateral hearing aid) Note: Randomization was stratified by clinical site.
Data source/how the data were collected	Screening information pulled from EHR data Baseline surveys captured via in-person interview and recorded in REDCap

Contact information for team member responsible for data collection/acquisition	All data access is through [REDACTED] [REDACTED]. Questions on data validity will go to PI: [name] ([contact])
Date or version (if downloaded, provide date)	10.17.2024
Data transfer method and date	Direct data extraction from REDCap
Where dataset is stored	REDCap Extracted data and analytic datasets are stored on a secure drive in the CRU folder: \\duhs-vclin-nc1\dusom_biostats_fs\Data\BiostatsCore\CRU\Head and Neck\[name]\PCORI_Pro00106077\Data pulls

Notes:

Description:
[insert]

3 Outcomes, Exposures, and Additional Variables of Interest

3.1 Outcome(s)

Outcome	Description	Variables and Source	Specifications
Switch configuration at 3 months	Patients are given the opportunity to switch configurations at 3 months.	ha_switch_3m	Binary: 1: Switched configuration 0: Didn't switch Switched configuration is defined as unilateral to bilateral or vice versa (do not count switching unilateral to a different ear as a switch) Switched configuration also includes switching from 1 or 2 to 0
APHAB Global Score	Global communication score at baseline, 3 months, 6 months	aphab_global_base aphab_global_3m aphab_global_6m	Rescore variables and multiply by 100 
 • 1 = 0.99 • 2 = 0.87 • 3 = 0.75 • 4 = 0.50 • 5 = 0.25 • 6 = 0.12 • 7 = 0.01 Reverse score questions 1, 9, 11, 16, 19, 21

			
Global score: mean of variables in the EC, BN, RV subscale scores (excludes questions 3, 8, 13, 17, 20, 22)
 
Also potentially used in other models as a covariate

APHAB – 4 subscales	EC, BN, RV, AV scales at baseline, 3 months, 6 months	aphab_ec_base aphab_ec_3m aphab_ec_6m aphab_bn_base aphab_bn_3m aphab_bn_6m aphab_rv_base aphab_rv_3m aphab_rv_6m aphab_av_base aphab_av_3m aphab_av_6m	Rescore variables and multiply by 100 
 • 1 = 0.99 • 2 = 0.87 • 3 = 0.75 • 4 = 0.50 • 5 = 0.25 • 6 = 0.12 • 7 = 0.01 
Reverse score questions 1, 9, 11, 16, 19, 21
 
EC: mean of questions 4, 10, 12, 14, 15, 23
 
BN: mean of questions 1, 6, 7, 16, 19, 24
 
RV: mean of questions 2, 5, 9, 11, 18, 21
 
AV: mean of questions 3, 8, 13, 17, 20, 22
 
Also potentially used in prediction models as covariates

